5.4.2.1 Summary and Incidence Analysis

Overall summary of AE table will be done for the LTE period and placebo-controlled and LTE active treatment period, presented by LTE treatment group. The following information will be summarized: the number of subjects with any AE, with any AE by maximum severity, the number of subjects with any related AE (related to study drug as assessed by investigator), the number of subjects with SAE, the number of subjects with related SAE, the number of subjects with AE leading to drug withdrawal, the number of subjects with AE leading to study withdrawal, and the number of subjects with a fatal event.

The sorting order of AE incidence tables, unless otherwise specified, will be by decreasing frequency order of “BIIB092 total” column within each category in the tables presented by LTE treatment group. A subject is counted only once within each category in each table. For example, for the table of AEs by system organ class and preferred terms sorted by decreasing frequency presented by LTE treatment group, system organ class will be presented in decreasing frequency order of BIIB092 total column, and within each system organ class, preferred terms will be presented in decreasing frequency order of BIIB092 total column. A subject is counted only once within each system organ class and preferred term.

CONFIDENTIAL

The information contained herein may not be used, disclosed, or published without the written consent of Biogen MA Inc.

The following AE incidence tables will be provided for the LTE period. Selected tables (marked with *) will be presented for incidence rate of AEs for the placebo-controlled and LTE active treatment period:

1. AEs by system organ class and preferred term sorted by decreasing frequency *
2. AEs by system organ class and preferred term sorted by alphabetical order
3. AEs by system organ class *
4. AEs at least 2% higher in incidence by system organ class and preferred term for early start BIIB092 2000 mg/4wk compared to late start BIIB092 2000 mg/4wk presented only for LTE period
5. AEs by preferred term *
6. AEs by preferred term with an incidence of 5% or more
7. AEs by maximum severity by system organ class and preferred term by decreasing frequency (System organ class will be presented alphabetically. Preferred terms will be presented in decreasing frequency order. Maximum severity will be presented within each preferred term in the order of mild, moderate, severe, unknown and total. A subject will be counted only once at the maximum severity within each system organ class and preferred term.)
8. AEs by maximum severity by preferred term
9. Severe AEs by system organ class and preferred term by decreasing frequency *
10. Severed AEs by preferred term *
11. Related AEs by system organ class and preferred term by decreasing frequency *
12. AEs related to tau PET ligand by system organ class and preferred term by decreasing frequency (using tau PET population)
13. SAEs by system organ class and preferred term by decreasing frequency *
14. SAEs by preferred term *
15. Related SAEs by system organ class and preferred term by decreasing frequency *
16. SAEs with fatal outcome by system organ class and preferred term by decreasing frequency
17. AEs that led to drug interrupted by system organ class and preferred term by decreasing frequency
18. AEs that led to discontinuation of study treatment by system organ class and preferred term by decreasing frequency
19. AEs that led to withdrawal from study by system organ class and preferred term by decreasing frequency
20. AEs related to lumbar puncture (LP) by system organ class and preferred term (using CSF population)

CONFIDENTIAL

The information contained herein may not be used, disclosed, or published without the written consent of Biogen MA Inc.

The following listings will be provided.

1. Listing of AEs
2. Listing of SAEs (including pre-dosing SAEs)
3. Listing of AEs that led to infusion interruption
4. Listing of AEs that led to discontinuation of study drug
5. Listing of AEs that led to withdrawal from study
6. Listing of AEs related to tau PET ligands
7. Listing of SAEs with fatal outcome
8. Listing of AEs related to lumbar puncture (LP)
9. Listing of death
10. Listing of pre-treatment AEs

5.4.2.2 Incidence Rate Analysis

Incidence rate of AEs based on the entire follow-up time for subjects with at least 1 AE in LTE period may be summarized by system organ class and preferred terms. The incidence rate tables will be presented by LTE treatment group. The entire follow-up time for LTE period is from the first dose in LTE period until the last day on study.

Follow-up adjusted incidence rate of AEs may also be summarized for placebo-controlled and LTE active treatment period, due to the different length of placebo-controlled and LTE active treatment period in early start versus late start high-dose BIIB002 subjects. The entire follow-up time is from the first dose in active treatment period (placebo-controlled period first dose of BIIB092 for early start subjects and LTE period first dose of BIIB092 for late start subjects) until the last day in the study.

5.4.2.3 Infusion Reactions

Please refer to the placebo-controlled period SAP for infusion reaction definitions. The same infusion reaction tables as described in placebo-controlled period SAP will be summarized for LTE period by LTE treatment groups.

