4.5.2. Potential Risks

The nonclinical studies conducted to date have demonstrated an acceptable safety profile for BIIB092 to support continued use in clinical studies.

As of 25 November 2018, an estimated 486 healthy participants or participants with PSP or AD have been exposed to BIIB092 in clinical studies. The following summary of the safety profile of BIIB092 is based on safety data from the completed Studies CN002001 and CN002003 and the ongoing Study 251PP201. In the SAD study in healthy participants, there were no safety findings of note, and development continued in patients with PSP. In participants with PSP, to date, the most commonly reported AEs were fall, urinary tract infection (UTI), contusion, and headache. Most AEs have been reported as mild or moderate in intensity. Serious AEs (SAEs) have generally been consistent with disease (UTI, respiratory arrest, aspiration pneumonia, and progressive PSP) or are not unexpected in the patient population enrolled in the trials

CONFIDENTIAL

The information contained herein may not be used, disclosed, or published without the written consent of Biogen MA Inc.

(cholecystitis, cancer, fractures, and anemia). There have been 3 deaths, all of which were likely related to underlying disease (respiratory arrest, aspiration pneumonia, and progressive disease). None of the SAEs or deaths were considered related to BIIB092 by Investigators. No safety concerns have been identified from laboratory, vital signs, or electrocardiogram (ECG) assessments. Nonserious infusion reactions have been observed and are an identified risk of BIIB092.

BIIB092 is a humanized IgG4 monoclonal antibody. While a low risk of immunogenicity is suggested by preclinical studies, the risk of immunogenicity in humans is unknown. Immunogenicity is an AE of special interest that is under monitoring in all ongoing studies. No safety data regarding this topic have emerged that would change the safety profile of BIIB092.

In general, BIIB092 has been well tolerated in the clinical study participants. There are no important identified or potential risks in the program. The safety profile is acceptable to continue development.

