10. DISCONTINUATION OF STUDY TREATMENT AND WITHDRAWAL OF PARTICIPANTS FROM THE STUDY

10.1. Discontinuation of Study Treatment

A participant must permanently discontinue study treatment for any of the following reasons:

- The participant becomes pregnant. Study treatment must be discontinued immediately, and the pregnancy must be reported according to the instructions in Section 15.4.1.
- The participant withdraws consent to continue study treatment.
- The participant experiences a medical emergency that necessitates permanent discontinuation of study treatment or unblinding of the participant's treatment assignment.
- The participant experiences an AE or SAE that does not resolve or requires continued treatment that meets exclusionary criteria.
- The participant experiences a severe infusion reaction
- At the discretion of the Investigator for medical reasons.
- At the discretion of the Investigator or the Sponsor for noncompliance with the terms of the protocol.

The primary reason for discontinuation of study treatment must be recorded in the participant's case report form (CRF).

All participants who discontinue study treatment prematurely will be asked to remain in the study and continue all protocol-specified visits and procedures for the period in which they discontinued treatment (i.e., placebo-controlled or LTE). Participants who discontinue treatment during the placebo-controlled period should be encouraged to attend at least the Week 24, Week 52, and Week 78/EOS Visits and who discontinue treatment during the LTE should be encouraged to attend at least the Week 80, 104, 116, 128, 152, 156, 176, 196, 200, 224, and 226/EOS Visits, depending on when treatment was discontinued, and undergo all the scheduled procedures. At a minimum, these visits should include assessment of AEs/SAEs and concomitant medications and key clinical assessments, including at least the CDR, MMSE, ISLT, ADAS-Cog 13, ADCS-ADL, and FAQ. Participants who discontinue study treatment prematurely, regardless of the treatment period, will be asked to return to the study site for a Follow-up Safety Visit 14 weeks after receiving the last dose of study treatment. See [Table 1](#), [Table 2](#), [Table 3](#), and [Table 4](#) for the Schedule of Activities.

CONFIDENTIAL

The information contained herein may not be used, disclosed, or published without the written consent of Biogen MA Inc.

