11.1.1. Placebo-Controlled Period

Randomized, blinded study treatment will be administered by IV infusion at the study site once every 4 weeks, beginning on Study Day 1 and continuing through Week 76, for a total of 20 infusions (see [Table 1](#)).

Participants will receive 1 of the following treatment regimens:

- low-dose BIIB092 - 125 mg once every 4 weeks or 375 mg once every 12 weeks and placebo at the other 4-week dosing visits to maintain the treatment blind
- medium-dose BIIB092 - 600 mg once every 4 weeks
- high-dose BIIB092 - 2000 mg once every 4 weeks
- placebo

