11.1.2. Long-Term Extension Period

In the LTE period, participants will receive BIIB092 beginning at Week 80 and continuing through Week 224. Participants who were randomized to receive BIIB092 during the placebo-controlled period will continue to receive BIIB092 at the dose they were randomly assigned. Participants randomized to receive placebo during the placebo-controlled period will receive BIIB092 at the high dose (2000 mg) during the LTE period.

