2 DESCRIPTION OF LONG-TERM EXTENSION (LTE) OBJECTIVES AND ENDPOINTS

2.1 Primary LTE Objective and Endpoint

The primary objective for the long-term extension (LTE) period is to evaluate the long-term safety and tolerability of BIIB092 in participants with MCI due to AD or with mild AD.

The primary safety endpoint that relates to this objective is the incidence of AEs and SAEs over the placebo-controlled period and LTE period of the study.

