3.2 Analyses Period

Depending on the purpose, different analyses will be conducted on the following study periods:

1. LTE period. Only data in the LTE period will be included in these analyses. This LTE analysis period will be applied to all the AE analyses, and the analyses will include all subjects who were dosed in the LTE period.
2. Placebo-controlled and LTE period. All the data in the placebo-controlled and LTE periods will be included in these analyses. This analysis period will be applied to analyses including, but not limited to all efficacy analyses and listings. The analyses will include all subjects who were dosed in the study including those who did not enroll into the LTE period. For example, line plot of CDR sum of box mean change from baseline over time. in the placebo-controlled and LTE period.
3. Placebo-controlled and LTE active treatment period. Active treatment period is defined as the study period(s) that a subject received BIIB092. For early start subjects – subjects who received BIIB092 in both placebo-controlled and LTE period, all the data (placebo-controlled and LTE periods) will be included in the analyses. For late start subjects – subjects who received placebo in the Placebo-controlled period and BIIB092 in the LTE period, only data in the LTE period will be included. This analysis period will be applied to majority of safety tables, and the analyses will include all subjects who were dosed in the study except for subjects who received only placebo in the placebo-controlled period and did not get dosed in the LTE period. An example is the incidence rate of adverse events in the placebo-controlled and LTE active treatment period.

Subjects to be included in a certain output is determined by both the analysis set and the analysis period. For example, the incidence table of adverse events in the LTE period will include subjects in the safety population for the LTE period, i.e., all randomized subjects who received at least one dose of study treatment in the LTE period. The incidence rate table of adverse events in the placebo-controlled and LTE active treatment period will include subjects in the safety population for the active treatment period, i.e., all randomized subjects who received at least one dose of study treatment in the active treatment period. In this SAP we do not separately define the analysis set in each analysis period.

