5.4.2.4 AE of Special Interest

Please refer to the placebo-controlled period SAP for AEs of special interest. The same tables as described in placebo-controlled period SAP will be summarized for LTE by LTE treatment groups.

	Statistical Analysis Plan Long-Term Extension Period	V1.0
---	--	-------------

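### The LTE SAP plans infusion-reaction tables for the LTE period only, so none of them counts all five LTE groups from first BIIB092 infusion, and the early-start and late-start columns sit at different stages of exposure.

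*SAP*

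**What the plan says.** Protocol 4.5.2 is explicit about the risk: "Nonserious infusion reactions have been observed and are an identified risk of BIIB092". On how it is tabulated, SAP 5.4.2.3 takes the definitions from the separate placebo-controlled SAP and then says "The same infusion reaction tables as described in placebo-controlled period SAP will be summarized for LTE period by LTE treatment groups".

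The primary LTE endpoint in SAP 2.1 is the "incidence of AEs and SAEs over the placebo-controlled period and LTE period of the study". SAP 3.2 defines three analysis periods. The third, the placebo-controlled and LTE active treatment period, starts at each participant's first BIIB092 dose. It leaves out only people who received placebo and were never dosed in the LTE. Of it the SAP says "This analysis period will be applied to majority of safety tables".

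AE data are shown for five LTE treatment groups plus a BIIB092 total (SAP 5.4.2). The groups are 125 mg every 4 weeks, 375 mg every 12 weeks, 600 mg, early-start 2000 mg and late-start 2000 mg. The late-start group had placebo first and meets BIIB092 for the first time in the LTE.

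Two protocol rules shape who is in the LTE columns. Section 10.1 lists, among the reasons for permanent discontinuation of treatment, "The participant experiences a severe infusion reaction". Section 8.3 asks LTE entrants to have completed the first period with at least 14 doses, unless the sponsor approves otherwise.

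**The concern.** A reader of the LTE infusion-reaction table will set early-start 2000 mg beside late-start 2000 mg. The SAP invites this: one of the LTE-period AE tables in 5.4.2.1 contrasts exactly those two columns. For infusion reactions the contrast is not like with like. The early-start column describes people well into treatment who were not removed for a severe reaction. The late-start column describes people meeting the drug for the first time. A difference between the columns could reflect stage of exposure and selection, and nothing about early versus late start.

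The late-start group is also the only body of 2000 mg first exposures outside the placebo-controlled period. Under the present wording, no dedicated table in the LTE SAP joins those first exposures to the ones in the early-start groups. An identified risk is thus reported over a narrower window than the primary LTE endpoint, and narrower than the window used for most other safety outputs.

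**Working it through.** **Infusion counts.** The protocol's own figure comes first. Section 11.1.1 has dosing every 4 weeks, "beginning on Study Day 1 and continuing through Week 76, for a total of 20 infusions". The count is (76 − 0)/4 + 1 = 20, which reproduces it. For the LTE, section 11.1.2 says "participants will receive BIIB092 beginning at Week 80 and continuing through Week 224"; at 4-week visits this is (224 − 80)/4 + 1 = 37. The ceiling over both periods is 20 + 37 = 57.

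**Where each column of the LTE table starts.**

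| Column | Earlier BIIB092 infusions | First LTE infusion of BIIB092 is number | Ceiling by end of LTE |
|---|---|---|---|
| 125 mg, 600 mg and early-start 2000 mg, every 4 weeks | up to 20 | 20 + 1 = 21 | 57 |
| 375 mg every 12 weeks | Weeks 0, 12, …, 72: 72/12 + 1 = 7 | 7 + 1 = 8 | not computed |
| Late-start 2000 mg | 0 | 1 | 37 |

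Under the 14-dose entry rule, and without sponsor approval of an exception, an every-4-weeks participant could enter at infusion 14 + 1 = 15. The range is therefore 15 to 21. The ceilings assume full protocol dosing. SAP 5.6.2 records that no participant reached Week 226, so actual LTE follow-up is shorter.

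**Composition of a total column.** The planned early-start number is 88 + 88 + 176 = 352 of 528, or 66.7%. The planned late-start number is 176 of 528, or 33.3%. With equal LTE entry across arms (an assumption), about two thirds of a BIIB092 total column would be people already exposed.

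**Which period the LTE SAP uses for its safety outputs.**

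| Output | SAP section | Active treatment period used? |
|---|---|---|
| Overall AE summary; starred AE rate tables | 5.4.2.1 | yes |
| Laboratory values, shifts, abnormalities | 5.4.3 | yes |
| C-SSRS | 5.4.4 | yes |
| ECG | 5.4.5 | yes |
| Vital signs | 5.4.6 | yes |
| Safety MRI | 5.4.9 | yes |
| COVID-19 AE tables | 5.4.10 | yes, with the LTE period |
| Anti-drug antibodies | 5.7.1 | yes |
| Infusion reactions | 5.4.2.3 | no, LTE period only |

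**Treatment emergence.** SAP 5.4.2 ties treatment emergence to the first LTE infusion and, unless otherwise specified, lets only treatment-emergent events into tables. Read literally, that drops early-start events from the placebo-controlled period even where a table is labelled with the active treatment period. Adding the period to 5.4.2.3 without changing the anchor would therefore not be enough.

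**The case against.** **First exposures are not missing altogether.** A reader might infer that no table anywhere gives the risk from first BIIB092 infusion. The documents do not support that. The late-start column of the LTE table does so for its own group. SAP 5.4.2.3 also refers to infusion-reaction tables in the placebo-controlled SAP, which presumably cover early-start first exposures against concurrent placebo. That SAP was not available, so its content cannot be checked. What remains is that it cannot contain late-start first exposures, which occur only in the LTE, and that the LTE SAP plans no dedicated table joining the two sets.

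**Other outputs give partial cover.** The starred AE tables run on the active treatment period, and the AE listings span the whole study with a period flag. The cover is incomplete. Those tables do not apply the infusion-reaction definition and inherit the LTE anchor for treatment emergence. They are also promised in 5.4.2.1 but only optional in 5.4.2.2.

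**No rule is broken.** SAP 3.2 applies the active treatment period to most safety tables, not all, and elsewhere assigns the LTE period to all AE analyses. A table labelled LTE that reports LTE events is not wrong. This stands, and it is why the point is an improvement and not an error.

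**Tolerance selection is limited.** Only a severe reaction forces permanent discontinuation. After a mild or moderate one, protocol 11.2.2 lets the infusion resume, so such participants can enter the LTE. The early-start columns are selected against severe reactors, not against all reactors.

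**AEs of special interest.** SAP 5.4.2.4 has parallel wording ("The same tables as described in placebo-controlled period SAP will be summarized for LTE by LTE treatment groups"), and a reader might extend the point to it. Protocol 15.3.2 names immunogenicity as the event of special interest, and SAP 5.7.1 already tabulates antibody responses over the active treatment period. The extension is not supported.

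**Size.** It is tempting to quote a fold-understatement for the total column. The documents give no reaction rates, and such a ratio partly measures longer observation. Suppose the risk is 5% in the first period of exposure and 5% in the later one, so that first exposure carries no excess. The LTE total is then 5.0%. Counted from first infusion it is 5%/3 + (2/3)(1 − 0.95²) = 1.67% + 6.50% = 8.17%, a ratio of 1.63. A fold figure would mislead, and none is offered.

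**Conclusion.** The point holds in a limited form. As written, SAP 5.4.2.3 reports an identified risk over the LTE period alone. Its early-start columns (from about infusion 21, or about BIIB092 infusion 8 for 375 mg every 12 weeks) and its late-start column (from infusion 1) are not comparable, and a BIIB092 total column mixes them at roughly two to one. This structural finding follows from the dosing schedule and the LTE entry rules and needs no assumed reaction rate. The two-to-one figure assumes the planned allocation and equal LTE entry. Infusion 21 assumes full earlier dosing. A total column in the infusion-reaction tables is inferred from the general AE display rule, because the table layouts sit in the placebo-controlled SAP. How far any reported percentage would move cannot be stated. The point does not call the placebo-controlled results or any clinical rule into question. It is a cheap improvement.

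**What to change.** In SAP 5.4.2.3:

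1. Keep the LTE-period tables, with a footnote that the early-start groups are already-exposed participants and that only the late-start group is counted from its first BIIB092 infusion.
2. Add the same tables for the placebo-controlled and LTE active treatment period, including everyone dosed with BIIB092 whether or not they entered the LTE.
3. For that period, define treatment emergence from first BIIB092, and align the definition in SAP 5.4.2.
4. Show infusion reactions by BIIB092 infusion number (for example first, second to third, fourth and later), with the number of participants receiving those infusions as the denominator. Exposure differs by design, up to 57 every-4-weeks infusions for early start against 37 for late start, so crude proportions over the whole period would not be comparable. Tabulating by infusion number also lets early-start and late-start 2000 mg be pooled or compared at the same stage.

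The cost is some SAP wording and a few extra tables from data already collected. No trial procedure or clinical rule changes. The downside is a slightly longer safety output.
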